Given these shortcomings in this evolving area of clinical research, a comprehensive characterization of myocardial injury in patients with COVID-19 infection and the identification of clinical predictors for its occurrence could allow the development of predictive models, thus helping clinicians in the disease phenotyping and the early assessment of the risk of unfavourable outcome and improving a fast determination of most appropriate treatments and clinical paths, efficient planning and use of clinical resources in terms of treatment type and units (such as intensive care or coronary intensive care). In addition, the identification of clinical predictors and/or protective factors for myocardial injury in COVID-19 infection may pave the way for the development of specific therapeutic strategies aiming to reduce the impact of myocardial injury on COVID-19-related morbidity and mortality. Finally, assessing the long-term cardiovascular impact of myocardial injury in COVID-19 infection could help clinicians in the prognostic stratification and the choice of therapeutic strategies in the post-acute COVID-19 phases, possibly identifying those patients that may need a more aggressive therapy and a closer follow-up.

A comprehensive characterization of myocardial injury in COVID-19 infection is still lacking, and no clinical predictors of myocardial injury has been identified yet. Moreover, the long-term cardiovascular outcome of myocardial injury in the post-acute COVID-19 phase is largely unknown. We thus hypothesize that:

- that clinical predictors and/or protective factors (including vaccination status) for myocardial injury in COVID-19 infection could be identified, thus allowing the development of predictive models that could help clinicians in the disease phenotyping,

the early assessment of the risk of unfavourable outcome and improving a fast determination of most appropriate management;

- that myocardial injury in COVID-19 patients could be associated with a worse clinical course characterized by higher incidence of in-hospital complications and need for escalation of therapies;
- that myocardial injury in COVID-19 patients could be associated with a worse angina status and quality of life as well as with a higher rate of adverse cardiovascular events in the post-acute COVID-19 phase, thus helping in the prognostic stratification of COVID-19 patients and identifying those that may need a more aggressive therapy and a closer follow-up.

OBJECTIVES

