Primary objective

To identify clinical predictors of myocardial injury in patients hospitalized for COVID-19 infection since the introduction of vaccines (i.e., March 1, 2021).

Secondary objectives

1. To evaluate if the presence of myocardial injury during the index hospitalization for COVID-19 is associated with a worse in-hospital clinical course in terms of in-hospital complications and need for aggressive therapies.
2. To evaluate if the presence of myocardial injury during the index hospitalization for COVID-19 are associated with a worse angina status and quality of life (evaluated using the Seattle Angina Questionnaire [SAQ] summary score (15)) at 12-months follow-up.
3. To evaluate if the presence of myocardial injury during the index hospitalization for COVID-19 predicts a worse clinical outcome in terms of major adverse cardiovascular events (MACE) (defined as the composite of cardiovascular death, ischemic heart disease [acute or chronic coronary syndromes], stroke/transient ischemic attack [TIA] and hospitalization for heart failure), dysrhythmias (defined as the composite of new-onset atrial fibrillation and/or ventricular arrhythmias), inflammatory heart disease (pericarditis and/or myocarditis) or thrombotic disorders (pulmonary embolism, deep vein or superficial vein thrombosis) at 12-months follow-up.

METHODS

Study design

Retrospective and prospective observational study.

Population

All consecutive patients hospitalized at Policlinico Universitario A. Gemelli IRCSS since March 1, 2021, with a diagnosis of SARS-CoV-2 infection (≥ 1 positive nasopharyngeal swab) and at least one value of high-sensitivity cardiac troponin I (hs-cTnI) measured during the index hospitalization will be enrolled. Given that the patients are unable to physically sign the informed consent form due to epidemiological reasons (contamination of papers by SARS-CoV-2), each patient will verbally declare the consent to “Consenso al trattamento dei dati personali e dei campioni biologici a scopo di ricerca – no profit”, “modulo di dichiarazione della volontà espresso ai fini del consenso informato generale alle cure” and “modulo dossier sanitario – richiesta di oscuramento/deoscuramento di eventi/episodi” at the presence of at least two witnesses.

Inclusion criteria

- Age ≥ 18 years;
- Overt COVID-19 infection (molecular nasopharyngeal swab positive for SARS-CoV-2 ≥ 1);

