- Patient with at least a high sensitivity Troponin I measured during hospitalization course.
- Available data on vaccination.
- Verbal informed consent

Exclusion criteria

- Age <18 years;
- Patient in whom at least one high sensitivity Troponin I value measured during the course of hospitalization is not available.
- No data available on vaccination status.

Variables and procedures

This study will make use of Data Mart COVID-19 developed within Generator Real World Data Unit. The Data Mart COVID-19 belongs to the family of the diagnostic and prognostic mini-bots developed within the Generator Real World Data Unit project in which artificial intelligence solutions (such as text mining) are adopted to automatically extract both structured and unstructured data from hospital databases of patients infected from SARS-CoV-2. Feature selection and machine learning algorithms can be applied to develop diagnostic and prognostic support systems for clinicians.

The specific data that which will be exploited are:

- Demographics data;
- Patient comorbidities, vital signs and symptoms at the time of admission;
- Laboratory analysis;
- In-hospital complications (e.g.: need for non-invasive or invasive ventilation, access to intensive care unit, length of hospitalization, use of glucocorticoids or antibiotics, death);

- Blood gas exchange information;
- Radiological reports;
- Medications at the time of admission, during hospitalization and at the time of discharge;
- Vaccination status.

Clinical follow-up

All patients will undergo a clinical follow-up by telephonic interview and/or clinical visit at 12 months from hospital discharge, during which the incidence of MACE, dysrhythmias, inflammatory heart disease and/or thrombotic disorders (both as incidence of the composite and as incidence of each individual components) in the past months will be investigated, the SAQ will be administered and the SAQ summary score will be collected.

ENDPOINTS

Primary endpoint

To assess for the presence of clinical predictors for the occurrence of myocardial injury, defined as at least one value of hs-cTnI >99th percentile upper reference limit (16), in patients hospitalized for COVID-19 infection.

Secondary endpoints

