All demographic, clinical and laboratory characteristics will be summarized by descriptive statistics techniques. In depth, qualitative variables will be expressed by absolute and relative percentage frequencies. Quantitative variables, indeed, will be reported either as mean and standard deviation (SD) or median and interquartile range (IQR), respectively in the case they were normally or not normally distributed. Their distribution will be previously assessed by the Shapiro Wilk test. Between groups differences in the demographic, clinical, laboratory and pathologic features will be assessed by the Chi Square or the Fisher's exact test as for qualitative variables, with Yates correction, as appropriate, whilst quantitative variables will be evaluated either by the Student's t test or the Mann-Whitney U test, according to their distribution. Univariable and multivariable logistic regression models will be performed to evaluate the presence of clinical predictors for the occurrence of myocardial injury in COVID-19 infection. Results will be expressed as odds ratio (OR) with 95% confidence interval (CI). Model calibration performances will be evaluated via the Hosmer-Lemeshow goodness of fit test with 10 groups. Model performance will be assessed through receiver-operator characteristic (ROC) curve analysis by reporting the area under the curve, sensitivity, specificity and +/- likelihood ratio (LR). Univariable and multivariable logistic regression analysis will be performed also to assess the association of myocardial injury in COVID-19 infection with in-hospital complications and need for aggressive therapies.

Univariable and multivariable multiple linear regression will be instead used to assess

whether SAQ summary score at 12-months follow-up is affected by myocardial injury in patients with COVID-19 infection.

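### One logistic analysis serves both prediction of myocardial injury and the question whether vaccination protects; if admission severity enters the model, its vaccine odds ratio can understate protection

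*Protocol*

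**What the plan says.** The first hypothesis, stated just before the Objectives, is that "clinical predictors and/or protective factors (including vaccination status) for myocardial injury in COVID-19 infection could be identified". The paragraph before the hypotheses gives such factors a use beyond prediction: "the identification of clinical predictors and/or protective factors for myocardial injury in COVID-19 infection may pave the way for the development of specific therapeutic strategies".

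The primary objective is worded as prediction: "To identify clinical predictors of myocardial injury in patients hospitalized for COVID-19 infection since the introduction of vaccines". Vaccination is nevertheless built into the design. The cohort starts when vaccines became available, and the inclusion criteria require "Available data on vaccination".

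Variables and procedures gives one undivided list of data to be used. Vaccination status stands in it with "Patient comorbidities, vital signs and symptoms at the time of admission", laboratory analysis, "Blood gas exchange information" and radiological reports. Only the vital signs and symptoms are tied to admission. No time point is given for the laboratory, blood-gas and radiology data.

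For injury as the outcome, the Statistical analysis section offers a single modelling approach: "Univariable and multivariable logistic regression models will be performed to evaluate the presence of clinical predictors". Results are ORs with 95% confidence intervals, and the model is judged by Hosmer-Lemeshow calibration and ROC measures. The covariates are not named, variables fixed before infection are not separated from those measured after it, and vaccination has no analysis of its own.

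**The concern.** A prediction model may use anything known at the time of prediction, including how ill the patient is on arrival. A model meant to show whether a factor protects should not adjust for what that factor changes. If vaccination makes the disease milder, and milder disease causes less injury, then vital signs, oxygenation, inflammatory markers and imaging at admission lie between vaccination and injury. With them in the model, the vaccine OR keeps only the association that does not pass through those measures. Restricting predictors to admission values does not help, because admission severity already follows vaccination.

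The univariable OR is no substitute. Where older and sicker patients are vaccinated more often, confounding works against an apparent benefit. Vaccine coverage and the disease itself may also shift over calendar time in a cohort that opens in March 2021.

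The risk is that a protective association in this cohort is reported as weak or absent because neither planned OR was built for that question.

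**Working it through.** The protocol gives no vaccination rate, vaccine effect, age gradient or covariate list, so there is no figure of its own to reproduce. The mechanism was tested by simulation. Every input below is an assumption, except the 25% event fraction (the protocol's worked example in Sample size calculation) and N = 2000 (its expected enrolment).

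**Step 1. Severity as intermediate, no confounding.**
- 60% vaccinated (V); severity S = −a·V + standard normal noise.
- logit P(injury) = b0 + ln(direct OR)·V + c·S, with b0 set to give 25% events.
- a = 0, 0.25, 0.5 or 0.8 SD; c = 0.5 or 1.0 per SD; direct OR 1.0, 0.8 or 0.6; 1,000,000 patients per scenario.
- Share of log OR removed = 1 − ln(OR with S) / ln(OR without S). Example (a = 0.25, c = 0.5, direct OR 0.8): 1 − ln(0.804)/ln(0.721) = 1 − 0.218/0.327 = 0.33.

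| Scenario | OR without S | OR with S | Share of log OR removed |
|---|---|---|---|
| a > 0, no direct effect | 0.89 to 0.51 | about 1.00 | about 100% |
| a > 0, direct OR 0.8 | 0.72 to 0.42 | about 0.80 | 33% to 74% |
| a > 0, direct OR 0.6 | 0.54 to 0.33 | about 0.60 | 16% to 54% |
| a = 0, direct OR 0.8 | 0.81 to 0.83 | about 0.80 | none |
| a = 0, direct OR 0.6 | 0.62 to 0.64 | about 0.60 | none |

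In the last two rows the adjusted OR lies slightly further from 1. That is non-collapsibility of the OR, which also enters the shares in the other rows. If an unmeasured cause of both severity and injury is added and there is no direct effect, the severity-adjusted OR moves above 1 (1.06 to 1.22).

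**Step 2. Age confounding added.**
- About 50% vaccinated, with the log odds of vaccination rising 0.8 per SD of age.
- S = −0.8·V + 0.3·age + noise; logit P(injury) = −1.4 + 0.8·S + 0.6·age (+ direct effect·V). Injury is about 20%.

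| Vaccine OR | Univariable | Age-adjusted | Age and severity |
|---|---|---|---|
| No direct effect | 0.96 | 0.56 | 1.00 |
| Direct log OR −0.2 | 0.81 | 0.47 | 0.82 |

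With no direct effect and N = 2000, the share of runs with p < 0.05 was 4% to 6% univariable, 99% to 100% age-adjusted and 5% with severity added (two sets of runs).

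**Step 3. How far this depends on the inputs (no direct effect).**
- Age-vaccination slope: from 0 to 1.5 per SD, the univariable OR runs from about 0.59 to about 1.2. The near-null 0.96 needs a slope close to 0.8. The severity-adjusted OR stays near 1.00 throughout.
- Measurement of severity: adjusting for a proxy with added noise of SD 1 gives 0.73 to 0.74 instead of 1.00.
- Selection into hospital: if admission depends on severity (selection slopes 1 and 2), the age-adjusted OR moves from 0.56 to about 0.6 and about 0.7.

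**The case against.** The strongest reply is that the protocol never says what is in the multivariable model. The list under Variables and procedures is the data extract for all objectives. It also contains in-hospital complications, death and discharge medication, so it cannot be the covariate set of this model. A separate statistical analysis plan may settle the covariates. This stands. A reader might infer that the planned model does adjust vaccination for admission severity and so removes its effect, but no section says so.

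Second, the primary objective and endpoint concern predictors, and the performance measures and the sample-size argument are those of a prediction model. Severity belongs in such a model, and in that language a protective factor may simply be a predictor with an OR below 1. This stands for the primary objective. It does not dispose of the hypothesis, which names vaccination as a possible protective factor and links such factors to therapeutic strategies. That question has no analysis suited to it.

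Third, full loss of the effect is an extreme case. It needs the whole effect to run through severity, and severity to be captured without error. A null result in both the univariable and the multivariable table also needs a particular strength of age confounding. Both limits stand.

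Fourth, every patient is hospitalised and had troponin measured, so the sample is already selected in part on severity. This also stands. It limits what any model here can say, including the one proposed below, but it is no reason to condition on severity a second time.

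**Conclusion.** The concern holds in conditional form. One logistic analysis is asked to predict injury and to judge vaccination as protective, and neither OR it yields is suited to the second task. If admission severity enters the multivariable model, the vaccine OR can understate the association acting through milder disease. Under the assumptions tried, the loss on the log OR scale runs from nothing (vaccination does not change severity), through 16% to 74% (part of the effect is direct), to nearly all of it (none is direct). The documents do not show where in that range this study would fall.

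The stronger readings, that the protective effect will be removed or that both tables will show no association, are not supported. The covariates are open, and those results arise only under chosen inputs. The prediction objective is not affected. The change is still worth making, because the hypothesis is explicit and the remedy nearly free.

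**What to change.** Keep the full multivariable model for prediction. In the Statistical analysis section:

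1. Add one logistic model for vaccination and myocardial injury, adjusted only for variables fixed before infection (age, sex, comorbidities, pre-admission medication) and for calendar period of admission. Leave out admission vital signs, symptoms, laboratory values, blood gases and radiology. Use its OR for the protective-factor hypothesis.
2. Label the vaccine OR from the full model as conditional on severity, and say that it is not the estimate of protection.
3. State that both ORs apply to hospitalised patients with a troponin measurement and do not estimate the effect of vaccination in the population.

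The cost is one extra model and a few sentences. Demographics, comorbidities, medication at admission and vaccination status are already in the list of data to be used. Admission date is not listed, but eligibility by date requires it.

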1. The occurrence of myocardial injury during the index hospitalization for COVID-19 infection will be correlated with in-hospital complications (defined as the composite of the need for non-invasive or invasive ventilation, access to intensive care unit, length of hospitalization, use of glucocorticoids or antibiotics, and death).
2. The occurrence of myocardial injury in patients during the index hospitalization for COVID-19 infection will be included in a prediction model and correlated with future cardiovascular events (MACE), dysrhythmias, inflammatory heart disease and/or thrombotic disorders at 12-months follow-up.
3. The occurrence of myocardial injury during the index hospitalization for COVID-19 infection will be correlated with angina status and quality of life, evaluated using the SAQ summary score, at 12-months follow-up.

STATISTICAL ANALYSIS PLAN

Sample size calculation

A comprehensive characterization of myocardial injury in COVID-19 infection is still lacking, and no clinical predictors of myocardial injury has been identified yet. Moreover, the long-term cardiovascular outcome of myocardial injury in the post-acute COVID-19 phase is largely unknown. Thus, this configures as a pilot study on large-scale cohort. As such no formal sample size calculation is needed. However, based on the COVID-19 datamart of our clinical institution and on inclusion criteria, we expect to include in the study around 2000 patients hospitalized with COVID-19. Such a sample size is largely consistent with common rules of thumb for pilot studies. In addition, the estimated sample size is largely consistent with the van Smeden metamodels related to the new statistical approaches for the development of clinical prediction models (17). The square root of the mean squared prediction error (rMPSE) and mean absolute prediction error (MAPE) may be approximated via the results of these. Lower values for rMSPE and MAPE indicate better performance. For instance, at a sample size of $N=400$, with $P=8$ candidate predictors and an expected event fraction of $\frac{1}{4}$, the predicted out-of-sample rMPSE would be 0.065 when ML model (without variable selection) is applied, and 0.053 for Ridge regression; MAPE would instead be 0.045 for the ML model and 0.038 for the Ridge regression.

Statistical analysis

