All RWD studies have research purposes and therefore consent-related procedures are consistent with European Directive 2016/679. The data architecture which supports RWD studies has been defined to provide the highest degree of protection, in accordance with all GDPR and security requirements. In this respect, RWD provides “protection by design” in each step of the process.

Significance and innovation

This study will provide a detailed characterization of myocardial injury in patients with COVID-19 and its role in determining the different clinical courses of SARS-CoV-2 infection. Moreover, the aim of study is to identify, for the first time, the clinical predictors of the occurrence of myocardial injury in patients with COVID-19 infection that could allow the development of predictive models as well as help clinicians in the early assessment of the risk of myocardial injury and the prevention of the associated unfavourable outcomes. Furthermore, this study will characterize the cardiovascular outcomes in the post-acute COVID-19 phase, and it will evaluate for the first time the long-term clinical outcomes of patients who experienced myocardial injury, possibly paving the way for the implementation of specific therapies aiming to reduce the cardiovascular risk and the long-term sequelae of COVID-19.

References

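### Calibration of the myocardial injury model rests on an in-sample Hosmer-Lemeshow test that cannot detect overfitting, and the ROC measures carry no optimism correction

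*Protocol*

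**What the plan says.** The protocol's Statistical analysis section plans logistic regression for the primary aim: "Univariable and multivariable logistic regression models will be performed to evaluate the presence of clinical predictors". Two sentences then fix how the model is judged. On calibration: "Model calibration performances will be evaluated via the Hosmer-Lemeshow goodness of fit test with 10 groups". On performance, ROC analysis is planned "by reporting the area under the curve, sensitivity, specificity and +/- likelihood ratio (LR"). No calibration slope, intercept or plot is named, and no bootstrap, cross-validation, split sample or shrinkage.

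Prediction is part of the purpose. Significance and innovation expects predictors "that could allow the development of predictive models as well as help clinicians in the early assessment of the risk of myocardial injury", and the hypotheses in the introduction say much the same. The Sample size calculation section says "we expect to include in the study around 2000 patients hospitalized with COVID-19" and supports this number with a framework for clinical prediction models. Its worked example has 400 patients, 8 predictors and an event fraction of 1/4: "the predicted out-of-sample rMPSE would be 0.065 when ML model (without variable selection) is applied, and 0.053 for Ridge regression". Ridge regression and out-of-sample error do not appear again in the planned analysis.

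**The concern.** A maximum-likelihood logistic model is tuned to its own data. Its score equations force observed and predicted events to agree overall, and they force the calibration slope in those data to equal 1. The Hosmer-Lemeshow statistic with 8 degrees of freedom allows for this fitting. In the development data it can therefore reveal a wrong model form, but not coefficients that are too large because too many were estimated. AUC, sensitivity, specificity and likelihood ratios computed on the same data are too favourable for the same reason.

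At stake are the calibration statement and the reported discrimination, which a reader would use to decide whether the model can support early risk assessment. An overfitted model gives risks that are too extreme in new patients and would still usually pass the planned test. The protocol also justifies its size by out-of-sample error, yet plans nothing that estimates it.

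**Working it through.** **Inputs from the protocol.** N = 2000. Event fraction 0.25, taken from the sample size illustration. Significance level 0.05. Hosmer-Lemeshow with 10 groups.

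**Assumptions.** The number of candidate predictors P for the real model and the true AUC are not given, so ranges are shown. The only count is the 8 in the illustration. The list in Variables and procedures is broad (for example "Patient comorbidities, vital signs and symptoms at the time of admission", plus laboratory, blood gas, radiology, medication and vaccination data), so 20 to 40 is plausible but assumed. An event fraction of 0.40 was also tried.

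**Quantities.**
- Optimism = apparent AUC − AUC of the same fitted model in new patients.
- Calibration slope = coefficient of the fitted linear predictor when the outcome in new patients is regressed on it. Below 1 means predictions too extreme.
- Hosmer-Lemeshow = Σ (O − E)² / [E(1 − E/n)] over 10 risk groups, with 8 df in the development data and 10 df in new patients.
- Positive LR = sensitivity / (1 − specificity), at the Youden cut-off (assumed, as none is named).

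**Step 1: the protocol's own figure.** ML was read as maximum likelihood. With N = 400, P = 8 and event fraction 0.25, simulation gave rMSPE 0.064 to 0.066 and MAPE 0.044 to 0.051 over true AUC 0.65 to 0.81. At AUC 0.78 the values were 0.0644 and 0.0459, against 0.065 and 0.045 stated. The example is reproduced (the ridge figures were not re-simulated). In a run of this same N = 400, P = 8 setting with true AUC about 0.71, apparent AUC was 0.722 and AUC in new patients 0.693, so optimism was 0.029. The slope in new patients was 0.85, while in-sample Hosmer-Lemeshow rejected in 5.0% of samples.

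**Step 2: the planned size.** N = 2000, 25% events (2000 × 0.25 = 500), independent normal predictors, 8 with equal true effects and the rest noise, all kept in the model, 300 runs per cell. The three entries per cell are for true AUC 0.66, 0.74 and 0.83; optimism is taken before rounding.

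| P | Events per predictor | AUC apparent / new | Optimism | Slope in new patients |
|---|---|---|---|---|
| 8 | 500/8 = 62.5 | 0.664/0.655, 0.746/0.740, 0.831/0.828 | 0.008, 0.006, 0.003 | 0.95–0.98 |
| 20 | 500/20 = 25 | 0.670/0.649, 0.750/0.736, 0.835/0.825 | 0.022, 0.015, 0.010 | 0.86–0.95 |
| 40 | 500/40 = 12.5 | 0.683/0.640, 0.758/0.728, 0.840/0.820 | 0.043, 0.030, 0.019 | 0.74–0.89 |

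At 40% events and P = 40, optimism is 0.036, 0.025 and 0.016, and the slope 0.77 to 0.92. Positive LR at 25% events and P = 40, apparent versus new: 1.80 vs 1.53, 2.30 vs 2.03, 3.20 vs 2.90. At P = 8: 1.68 vs 1.58, 2.20 vs 2.10, 3.09 vs 2.96.

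**Step 3: what the planned test shows.** In-sample Hosmer-Lemeshow rejected in 3 to 6% of runs in all 18 cells (three P, three AUCs, two event fractions). The same fitted models in 2000 new patients were rejected in 13–20% (P = 8), 18–28% (P = 20) and 39–63% (P = 40). The true model, as reference, was rejected in 4 to 5%.

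**Step 4: a different design.** With 6 true predictors, true AUC about 0.71, N = 2000 and 25% events, results for P = 8, 30 and 60 were:
- optimism 0.004, 0.025 and 0.050;
- slope in new patients 0.97, 0.86 and 0.74;
- in-sample rejection 5.0%, 2.5% and 4.5%, against 17%, 40% and 84.5% in new patients;
- after a univariable p < 0.05 screen, optimism 0.005, 0.013 and 0.017, and slope 0.98, 0.93 and 0.92.

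A further run with such a screen at P = 40 gave optimism 0.008 to 0.021 and slope 0.87 to 0.96.

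**Step 5: does the remedy work?** Bootstrap with 100 resamples on 40 data sets, 25% events, P = 40. AUC apparent / corrected / new: 0.685/0.646/0.638, 0.759/0.732/0.728, 0.840/0.822/0.821. The share of optimism removed is 0.039/0.047 = 83%, 0.027/0.031 = 87% and 0.018/0.019 = 95%. Slope corrected versus new: 0.78/0.73, 0.86/0.85, 0.90/0.91. A small residual remains when the signal is weak.

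**Step 6: what Hosmer-Lemeshow is good for.** With P = 8 and an omitted squared term in the standardised linear predictor, the in-sample test rejected in 19–52% of runs at coefficient 0.15 and 66–100% at 0.30. It has a use as a check of gross misfit.

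**The case against.** The strongest objection is that this is an omission. Internal validation is often left to a separate SAP, which may exist, and the missing optimism correction alone would not be a fair criticism of a protocol. Moreover, no measure computed on the development data detects overfitting: the apparent calibration slope was 1.00 in every setting of Step 4, so what is missing is resampling, not a better test. Both points are right, and the second shapes the fix. They do not clear the plan, because the protocol positively fixes a calibration method and names no other, while invoking predictive use and out-of-sample error.

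A second objection is that the primary aim is to identify predictors, reported as odds ratios, and that nowhere does the protocol say a non-significant test will be read as good calibration in new patients. This stands in part: the odds ratios are untouched. But the test is named as the assessment of calibration, so its result will be the study's calibration statement.

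Third, the harm depends on assumed inputs. At the only predictor count in the document the AUC effect is trivial. The cells with 20 and 40 predictors force pure noise variables into an unpenalised model, and univariable screening roughly halves the optimism or better at 30 predictors and above. This stands as a limit on size, not on direction. Finally, at 8 predictors the test rejects in 13–20% of new samples although the slope is 0.95 to 0.98, so rejection rates do not measure practical importance. The slope and AUC should be used for that.

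**Conclusion.** The concern holds. The one calibration measure the protocol fixes does not respond to overfitting in the data used to fit the model, and the ROC measures would be optimistic. This blindness does not depend on the assumed inputs: in-sample rejection stayed near 5% in every design tried at 2000 patients.

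The consequence does depend on them. At 2000 patients and 8 predictors it is negligible for AUC (under 0.01). With 20 to 40 predictors all retained, at 25% events and true AUC 0.66 to 0.83, AUC is overstated by 0.010 to 0.043 and the slope in new patients is 0.74 to 0.95. Screening makes both smaller. The primary odds ratios of a prespecified model are not affected. The change should be made, but the matter is moderate and does not endanger the study.

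**What to change.** In the Statistical analysis section, stop resting calibration on the Hosmer-Lemeshow test and attach internal validation to every performance measure. Suggested wording:

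> *Calibration will be assessed by the bootstrap optimism-corrected calibration slope and intercept and a smoothed calibration plot; the 10-group Hosmer-Lemeshow test will be given as a supplementary check. AUC, sensitivity, specificity and positive and negative LR will be given as apparent and as bootstrap optimism-corrected values, with the choice of cut-off, and any variable selection if used, repeated in each resample.*

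The resampling is the essential part; an apparent slope or plot alone would not help. Keep the planned odds ratios with 95% CI.

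The cost is two sentences and some computing time, with no new data. The reported AUC and likelihood ratios will be slightly less favourable, with almost no change in AUC if the model has about 8 predictors.
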